9.2 Selection and Screening

Prior to commencement of any screening procedures, the PI, or designee, will inform the participant about the nature and purpose of the study, including the risks and benefits involved, possible AEs, the

fact that their participation is voluntary and provide a copy of the HDEC (or local equivalent)-approved Informed Consent Form for review. Each participant will acknowledge receipt of this information by giving written informed consent for their involvement in the study in the presence of the PI, or qualified designee, who will also sign and date the Informed Consent Form. Time of consent will be recorded on the Informed Consent Form. The original signed consent form will be retained by the PI and a copy of the original will be given to the participant. Informed consent will be performed per the Principles of the International Conference on Harmonisation (ICH) Good Clinical Practice (GCP) procedures.

Having given Informed Consent, potential participants will undergo procedures outlined in the Schedule of Assessments, to be performed within 60 days of the scheduled dosing date, to determine that he/she meets the inclusion/exclusion criteria specified in Sections 7.2 and 7.3.

9.3 *On-Study Procedures/Assessments*

9.3.1 *Study Procedures: Clinical Facility Confinement*

Eligible participants will present at the Clinical Facility on Day -1, the day prior to dosing. Note that study dose administration is on Day 1, which must occur within 60 days of screening. NHV participants only will be confined to the clinical facility until after the 24-hour post-dose (Day 2) assessments.

On arrival at the clinical facility on Day -1, the PI, or appropriately trained designee, will meet with participants to reiterate all study procedures and encourage participants to ask any questions. All participants shall undergo a check-in procedure during which questions will be asked regarding protocol compliance and safety monitoring.

Documentation of the participant's fulfillment of the entry criteria, for all participants considered for the study and subsequently included or excluded, is to be completed by the PI, or medically qualified designee. Documentation of screening failure details will be recorded using eligibility screening forms or a participant screen failure log. Procedures outlined in the Schedule of Assessments will be performed. Meals and water will be provided while participants are confined at the clinical facility. Timing will abide by fasting restrictions outlined in Section 7.5.

9.3.2 *Demographics/Medical History*

Medical History will include medication use over the previous 30 days, including vitamins, over-the-counter, prescription drugs, recreational drugs or supplements and alcohol and tobacco use.

9.3.3 *Physical Exam*

A complete physical exam will be performed at Screening and as per Schedule of Assessments.

At Screening, height (centimetres, without shoes) and weight (kilograms, without shoes) will be obtained to determine BMI.

At all other time points outlined in the Schedule of Assessments, a symptom-directed physical exam will be performed if indicated.

9.3.4 *Electrocardiogram*

A single 12-lead ECG measurement will be obtained at time points outlined in the Schedule of Assessments after the participant is supine for at least 3 minutes. Any abnormal ECGs will be repeated in triplicate, with each measurement approximately 1 minute apart. ECGs will be performed prior to venipuncture and other invasive procedures.

9.3.5 *Vital Sign Assessments*

Systolic/diastolic blood pressure, temperature, heart rate, respiratory rate (breaths/min) will be obtained at time points outlined in the Schedule of Assessments after the participant is seated or semi-supine for at least 3 minutes. Vitals signs will be obtained prior to venipuncture and other invasive procedures.

9.3.6 *Clinical Laboratory Tests & Pharmacodynamic Values*

Blood and urine samples will be collected to perform clinical laboratory tests run at a central laboratory. Participants will be required to fast for the Screening sample collections.

At the Screening visit, up to 60 days prior to the first dose of study medication, a blood and urine sample will be collected for the laboratory tests detailed below, to establish eligibility for enrolment. Baseline values will be the values from Day 1 pre-dose labs. If this sample is not available Screening values will be considered baseline. The results will be assessed by the PI, or medically qualified designee, before study enrolment. Any abnormality in laboratory values (that are confirmed on repeat) deemed clinically significant by the PI, or medically qualified designee (i.e., those that would jeopardize the safety of the participant or impact on the validity of the study results), will result in exclusion of that participant. Up to two retests for inclusionary or exclusionary labs are allowed. Clinical laboratory tests will be performed on participants' blood and urine at specified time-points listed in the Schedule of Assessments.

Biochemistry: Sodium, potassium, chloride, bicarbonate, glucose, urea, creatinine (including calculated creatinine clearance), creatine kinase, uric acid, phosphate, total calcium, anion gap, cholesterol, albumin, globulins, protein, total bilirubin, conjugated bilirubin, gamma

glutamyltransferase (GGT), alkaline phosphatase (ALP), alanine aminotransferase (ALT), aspartate transaminase (AST), lactate dehydrogenase (LD), triglycerides, amylase, lipase, C-reactive protein and Troponin I.

Hematology: Hemoglobin, red blood cell count (RBC), hematocrit, mean cell volume (MCV), mean cell hemoglobin (MCH), mean cell hemoglobin concentration (MCHC), platelets, white cell count, neutrophils, lymphocytes, monocytes, eosinophils and basophils.

Coagulation: Partial thromboplastin time (PTT), Prothrombin time (PT) with INR.

Urinalysis: Leucocytes, nitrites, urobilinogen, protein, pH, blood, specific gravity, ketone, bilirubin and glucose.

Reflex microscopic urinalysis will be performed if indicated: White Blood Cells, Red Blood Cells, Epithelial cells, Bacteria.

Serology: HBV genotyping, HBV-RNA (if scientifically feasible), HBV-DNA, HBsAg (qualitative and quantitative), Anti-HBsAg (qualitative and quantitative), HBeAg (qualitative and quantitative), Anti-HBeAg (qualitative and quantitative), HBcrAg (quantitative), Hepatitis C antibody and HIV antibody screen. If necessary, participants will be counseled by the PI, or medically trained designee, concerning the blood tests for Hepatitis B surface antigen, Hepatitis C and HIV antibodies, and their subsequent results.

HBV DNA sequencing: To be analyzed only if HBV DNA serum levels are above 60 IU/mL for ARO-HBV target site, HBsAg epitope shift, and core/pre-core mutation tests, and above 1,900 IU/mL for HBV deep sequencing. An additional sample will be collected if resistance is suspected (defined as a > 1.0 log IU/mL increase in HBV DNA from NADIR from Day 1 through day 71, confirmed by repeat test).

FSH: Post-menopausal status will be confirmed by follicle-stimulating hormone (FSH) level consistent with post-menopausal state.

Drugs Screen: Urine drug screen for Benzodiazepines, Amphetamines, Barbiturates, Methamphetamines, Methadone, Opiates, Phencyclidine, Cannabinoids, Ecstasy and Cocaine.

Pregnancy: Females of childbearing potential will have a urine pregnancy test. If urine pregnancy test is positive, patient will be referred to their primary care provider for follow up.

Cytokines & Complement: Samples for analysis of Cytokine Panel A: IL-6, MCP-1, TNFalpha, IL-8, IL-1beta, IFNalpha, IL-10, IL-12 (p40), IL-12 (p70), Mip-1alpha) and Complement factors (Bb and CH50, C5a, C4a, C3a) and Cytokine Panel B: TNF alpha, IFN gamma, CXCL-9, and CXCL-10 will be obtained as indicated at time points outlined in the Schedule of Assessments. Collected cytokine Panel B samples will only be analyzed at discretion of and with notification by Sponsor.

Anti-Drug Antibodies: For Cohorts 2b, 3b, 4b, 5b, 6, 7, 8, 9, 10 and 11 blood samples for the anti-drug antibodies test will be collected at Screening, Day 57 and Day 113 or at EOS.

Cellular Immunology Studies: For all CHB patient cohorts, blood samples to evaluate changes in anti-viral host immunologist profile will be collected on Day 1 (pre-dose), 43 and 113. This will include T cell subsets (activation and exhaustion state), NK cell subsets (activation and exhaustion state), B cell subset, monocyte subsets and HBV antigen specific T cell response (including HBeAg,

HBsAg). Cellular immunology studies will be conducted if scientifically feasible in New Zealand only.

Interferon Response Gene SNP testing: Patient's interferon response gene SNPs will be evaluated (if patient consents to limited genetic testing). A blood sample for pharmacogenomics (DNA) research is optional and will only be collected from subjects who consent separately to this component of the study. Subjects who are enrolled in the study at the time of this amendment will be contacted to ask for their consent for this component of the study. Sample can be collected any time after the consent has been signed. This sample can be used to assess impact of IL28B polymorphism on efficacy of ARO-HBV treatment. In addition, samples can be used to investigate the potential association of genetic factors with efficacy, safety, or pharmacokinetics of ARO-HBV, CHB infection, or HBV-related disease or may be used to develop tests/assays related to ARO-HBV or HBV. These analyses will be performed at the sponsor's discretion, will always be under the sponsor's supervision, and may be reported separately.

9.3.7 *Pharmacokinetics*

Samples for analysis of circulating AD04872 and AD05070 will be obtained at time points following the end of injection outlined in the Schedule of Assessments.

Plasma concentrations of ARO-HBV, NUC and JNJ-6379 will be measured at a single post-dose time point in Cohort 12 only.

9.3.8 *Concomitant Medications/Therapies*

Participants will be instructed to inform the PI of the details (indication, dose and dates of administration) if they do take any medication, and these details will be recorded in the eCRF. If necessary, paracetamol may be used during the study as necessary. Any other medication or therapy other than blood pressure medication must be approved by the Medical Monitor or PI prior to administration.

9.3.9 *Follow-Up Procedures*

Day 90 (± 5 days) Telephone Call

Documented telephone contact with each participant to verify compliance with contraceptive measures and absence of any known pregnancy at 90 days post EOS (Day 29 for NHVs and Day 113 for CHB patients).

Additional CHB Follow-up

With the exception of Cohort 12 patients, all other CHB patients consenting to additional follow up will be followed as per Additional Follow-Up Schedule of Assessments (Table 1.5), every 56 days (± 5 days) for 5 additional visits after Day 113. Only Cohort 12 patients will require follow-up until the Day 337 (±5 days) visit. Subjects consenting to additional follow up will continue on NUCs.

Subjects not consenting to additional follow up will be followed per protocol based on Schedule of Assessment Tables 1.2, 1.3 and 1.4.

9.3.10 *Early Termination Procedures*

The reason for Early Termination will be documented in source documents and eCRF. Procedures as outlined in the Schedule of Assessments will be completed.

9.4 *Allocation of Formulations*

Four NHV participants will receive active treatment and 2 participants will receive PBO in each dose level. Treatments will be administered per the randomized sequence kept by the pharmacy or in a secure place at the clinical site, under control of the un-blinded staff member. All CHB patients will receive active treatment. CHB patients in Cohort 12 will receive daily oral JNJ-6379 + ARO-HBV Q28 x 3.

9.5 Study Formulation Administration

Appropriately trained employees of the clinical site will administer ARO-HBV/PBO. Each dose will be administered as a subcutaneous injection. Doses of 400 mg will be administered as two injections per dose with each injection administered into separate a site. The date, time and location of administration will be recorded in the source notes and witnessed by a second person from the clinical facility. The preferred site of injection is the abdomen. Optional additional sites are the upper arms and thighs or other sites based on PI clinical judgement.

Table 2: Injection number and volume per cohort

Cohort	Dose	Concentration	Total Injection Volume	# Injections per planned dose
1	35 mg	200 mg/mL	0.175 mL	Single
1b	25 mg	200 mg/mL	0.125 mL	Single
1c	50 mg	200 mg/mL	0.25 mL	Single
2, 2b, 6, 7	100 mg	200 mg/mL	0.5 mL	Single
3, 3b, 10, 12	200 mg	200 mg/mL	1.0 mL	Single
4, 4b, 8, 9, 11	300 mg	200 mg/mL	1.5 mL	Single
5, 5b	400 mg	200 mg/mL	2.0 mL	Two (at separate sites)

JNJ-6379 will be dispensed to patients in Cohort 12 only who will take their daily dose (250 mg oral) at home. Patients will bring all remaining tablets to their subsequent visits for compliance assessment, and receive additional tablets to cover their daily doses until the next subsequent visit.

9.6 Timing of Treatments and Procedures

Actual times of procedures for each participant will vary depending on scheduling and will be recorded in the eCRF.

Post-dose time points will be determined based on time of injection.

In the event of multiple procedures scheduled at the same time, non-invasive procedures (i.e. ECGs, AE assessment) will be conducted prior to invasive procedures (i.e., blood sample collection). Timing of activities may be adjusted slightly to accommodate all procedures.

The following windows are allowed for study assessments/visits:

Pre-dose:	Within 60 minutes prior to dosing
PK/PD through 6 hours:	± 2 minutes
All other procedures through 6 hours:	± 10 minutes
PK/PD from 8 to 48 hours:	± 5 minutes
All other procedures from 8 to 48 hours:	± 15 minutes
Day 8:	± as per SOA
Day 15 to Day 29:	± as per SOA
Visits beyond Day 29:	± as per SOA

9.7 *Safety Endpoints*

The safety of ARO-HBV (alone or in combination with JNJ-6379) will be evaluated by collection of the following measurements performed at specified time points:

- Monitoring of AEs/ SAEs
- Physical examinations
- Vital signs
- ECG measurements
- Injection Site Reactions (Mild, Moderate or Severe): Photographic images will be taken of all injection site reactions at the time of reporting and at the time of resolution.
- Clinical laboratory tests (hematology, biochemistry, coagulation, urinalysis)
- Concomitant medications/therapy, and
- Reasons for treatment discontinuation due to toxicity

The AE/SAE reporting period for an enrolled participant will begin when the participant provides informed consent. Treatment-Emergent AEs/SAEs will be those defined as following dose administration. All AEs/SAEs that occur during the AE reporting period specified in the protocol must be reported to Arrowhead Pharmaceuticals, Inc., regardless of the relationship of the AE to study

treatment. Any known untoward event that occurs beyond the AE reporting period that the PI considers an SAE and possibly related to study treatment will be reported to Arrowhead.

9.8 *Blood Sampling for Pharmacokinetic and Pharmacodynamic Analysis*

Blood samples will be collected from participants through an indwelling cannula or through a fresh vein puncture. The actual blood collection time will be recorded in the source documents. All deviations outside the range allowed above will be documented as protocol deviations. In all such cases, appropriate time corrections, for the actual time of sample collection will be incorporated at the time of data analysis. Blood samples for pharmacokinetic and pharmacodynamic analyses will be collected at time points outlined in the Schedule of Assessments.

The target sample times will be printed in the eCRF. The actual sample times (times samples taken) will be recorded alongside the nominal times in the eCRF and will be entered at the time of or as soon as possible after sampling. All times must be recorded in the 24-hour format. An explanation must be given for any blood sample taken outside of the set sampling times.

9.8.1 Sample Processing and Analysis for Pharmacokinetic Samples

Blood samples will be collected and processed per the Laboratory Manual.

Plasma samples will be assayed by a validated hybridization-ligation method. The criteria for repeat analysis, as defined in the respective in-house procedure, will be followed.

The validation study conducted by the appointed bioanalytical laboratory to establish validity including accuracy, precision, reproducibility, specificity, recovery and frozen stability of the analytical method will be appended to the final report.

9.8.2 Sample Processing and Analysis for Pharmacodynamic, Cytokine and Complement Samples

Whole blood will be collected at specified time points for analysis of cytokines and complement.

Cytokines: Whole blood samples will be collected and processed per the Laboratory Manual. Initially the pre-dose and 2-hour post-dose samples will be analyzed, with the remaining samples analyzed if a change from baseline is observed at 2 hours.

Complement: Venous blood samples will be collected and processed per the Laboratory Manual at each time point. Initially the 0 (pre-) and 2-hour post-dose samples will be analyzed, with the remaining samples analyzed if a change from baseline is observed at 2 hours.

Results, percent change, and duration of response from baseline to 4 weeks (or longer as necessary) will be analyzed and summarized by dose cohort and treatment group.

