- Patient immune cell profile: T cell subsets (activation and exhaustion state), NK cell subsets (activation and exhaustion state), B cell subset, monocyte subsets. *To be conducted if scientifically feasible.*
- HBV antigen specific T cell response (including HBcAg, HBsAg). *To be conducted if scientifically feasible.*

Virology assessments (CHB patients only)

Virology assessments will be performed at specified time points per the Schedule of Assessments and will include the following:

- Qualitative assessments: HBsAg, HBeAg, anti-HBs, anti-HBe
- Quantitative assessments: HBV DNA, qHBsAg, qHBeAg, qHBcrAg, qHBV RNA (if feasible), anti-HBs and ratio of bound/free anti-HBs
- HBV genotyping and HBV sequencing

Immunogenicity:

For Cohorts 1b, 1c, 2b, 3b, 4b, 5b, and 6-12 blood samples for the anti-drug antibodies test will be collected at screening, Day 57 and Day 113 or at the end of study visit.

Pharmacokinetics (NHVs only and limited PK in Cohort 12):

Blood samples will be collected from each subject for pharmacokinetic analysis after dose 1 (Cohorts 1-5) per the Schedule of Assessments and for Cohort 12 patients per the Schedule of Assessments.

Genetic Testing (CHBs only):

If subject consents to genetic testing while actively participating in the study, one whole blood sample will be

collected on Day 1 or any time thereafter for SNP analysis for IFN response genes.

Cytokines:

Blood samples will be collected from each NHV participant for cytokine analysis per the Schedule of Assessments. The resultant serum will be analyzed for the following cytokine panel A: IL-6, MCP-1, TNF-alpha, IL-8, IL-1beta, IFN alpha, IL-10, IL-12 (p40), IL-12 (p70), and Mip-1alpha. CHB patients will have cytokine panel B (TNF alpha, IFN gamma, CXCL-9, and CXCL-10) measured as per Schedule of Assessments. In Cohorts 1-5 (Panel A), initially the 0 (pre-) and 2-hour post-dose samples will be analyzed, with the remaining samples analyzed only if a change from pre-dose baseline is observed at 2 hours.

Complement:

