* Repeat if > 2 weeks from Screening

1. Symptom-directed PEs to be performed by visit as necessary.

2. ECGs: Measured pre-dose and at 1 and 2 hours post-dose; more frequently per hour if necessary. Performed prior to other invasive procedures.

3. PK: (plasma) Blood samples collected 0 (pre-dose), 15 min, 0.5, 1, 2, 3, 6, 24 & 48 hours post-dose

4. Cytokines Panel A only in NHVs): (whole blood). Serial venous blood samples collected 0 (pre-dose) 0.5, 2, 6, & 24 hours after dosing.

5. Complement: (serum and plasma). 2 venous blood samples collected 0 (pre-dose), 0.5, 2, 6 & 24 hours after dosing.

6. Vitals: Measured pre-dose and at 5 min, 0.5, 1, 2, 3, and 6 hours post-dose.

7. Meals: Lunch, Dinner, and snack on Day 1 at approximately 2 hours, 6 hours and 8 hours post-dose. Breakfast optional on Day

8. Urine pregnancy test for females of childbearing potential only.

9. AE/SAE data capture begins from time of informed consent.

10. Clinical Chemistry, Hematology, Coagulation and Urinalysis pre-dose and at 6 hours post-dose.

11. Performed for females not of childbearing potential to confirm postmenopausal status

12. Pre-dose

13. Cohorts 2-5 only Metabolite ID: Blood samples collected 0 (pre-dose), 0.5, 1, 3, 6, 24 & 48 hours post-dose

14. **Cohorts 2-5 only:** Collect spot urine samples on days 1 (pre-dose), 8, 15, and 29 and aliquot into 3 aliquots and freeze and store at -80C. Collect all urine from 0-6 hours and 6-24 hours after dosing. Aliquot each collection into three aliquots and freeze and store at -80C. Discard the remainder of the collected urine.

Table 1.2: Cohorts 1b, 1c, 2b, 3b, 4b, 5b, 8 and 9 (CHB patients, three Q28 day doses)

Assessment	Screen (Days -60 to -1)		Day 1	Day 2	Day 8	Day 15 (± 2)	Day 29, 57 (± 2)	Day 43, 71 (± 2)	Day 85 (± 2)	Day 113 (± 2) EOS	Early Termination
Informed Consent	X	RANDOMIZE									
Eligibility Criteria	X		X ⁹								
Body Mass Index	X										
Demographics	X										
Medical History	X		X*								
Drug Screen	X										
Hepatitis/HIV Serology Screen	X										
Physical Exam ¹	X		X*	X ¹	X ¹	X ¹	X ¹	X ¹	X ¹	X	X ¹
FSH	X ⁸										
Pregnancy test	X ⁵		X ⁵				X ⁵			X	X
ECG	X		X ²				X ²			X	X
Vital Signs (BP, temp, RR, heart rate)	X		X ⁴	X	X	X	X ⁴	X	X	X	X
Hepatic Fibrosis Measure (FibroScan®)	X										
Clinical Labs (heme, coag, chem, UA)	X		X ⁷	X	X	X	X ⁷	X	X	X	X
HBeAg qualitative	X										
Quantitative HBsAg, HBcrAg, HBeAg (e+ only) HBV DNA, HBV RNA	X		X		X	X	X	X	X	X	X

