The whole blood collected for analysis following a single dose of ARO-HBV at different dose levels will undergo analysis for cytokines (Panel A) and complement changes. Results, percent change, and duration of response from baseline to 24 hours (or 48 hours, as necessary) will be analyzed where indicated by initial testing at pre-dose and at 2-hours post-administration. If cytokine or complement levels are elevated from pre-dose to 2-hours post-dose then all other specified timepoints (See Schedule of Assessments) will also be analyzed. Whole blood collected following multiple doses of ARO-HBV for cytokine Panel B samples will only be analyzed at discretion of and with notification by Sponsor. Results, percent change, and duration of response from baseline will be analyzed where indicated. Results for cytokines and complement will be summarized by dose cohort and treatment group.

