### 3. STATISTICAL CONSIDERATIONS

Data will be handled and processed according to the sponsor's representative (Novotech (Australia) Pty Ltd) Standard Operating Procedures (SOPs), which are written based on the principles of GCP.

All data collected on the eCRFs will be presented in the data listings and will be listed and sorted by subject number and visit, where applicable. All summaries will present the data by ARO-HBV dose level/cohort and overall (total subjects), as applicable.

Data collected during the main study (up to the Day 29 or Day 113 EOS visits) and at the additional follow-up visits (CHB cohorts only) will be presented in the same summary table, as appropriate. The first part of each table will present the main study results for the specific analysis. The second part of each table will include all data collected during the study, including data collected during the follow-up period, for the subset of CHB patients that consented to participate in the follow-up. All data will be included in the listings, and data collected during the follow-up period will be flagged in all event/medication-based listings. Separate figures that include all data will be presented for the subset of patients that participated in the follow-up period.

Unless otherwise stated, the following statistical approaches will be taken:

- Continuous variables: Descriptive statistics will include the number of non-missing values (N), mean, standard deviation (SD), median, minimum, maximum.
- Categorical variables: Descriptive statistics will include frequency counts and percentages per category. Percentages will be rounded to one decimal place, with the denominator being the number of subjects in the relevant population with non-missing data, unless otherwise specified.
- Imputation: No missing data will be imputed generally.
- Confidence intervals (CIs): CIs will be two-sided and will use 95% confidence levels unless specified otherwise.
- Baseline: Baseline values will be defined as the last non-missing observation (pre-dose value closest to the first dose) for each subject prior to the dosing of study medication (i.e. start of injection on Day 1).
- Repeat assessments (Safety): If there is a repeat test, the repeat result will be used in the analysis table and the original result will only be listed in the data listing.

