#### **14. CYTOKINES AND COMPLEMENT**

Cytokines Panel A (whole blood, NHV cohorts only) will be collected at the time of 0 (pre-dose), 15 min, 0.5, 1, 2, 3, 6, 24 and 48 hours post-dose. Cytokines Panel B (whole blood, CHB cohorts only) will be collected across the study period according to the protocol schedule of assessment,

Complement (serum and plasma, NHV cohorts only) will be collected at the time of 0 (pre-dose), 0.5, 2, 6 and 24 hours post-dose.

Cytokines (Panels A/B) and complement data will be analyzed using the PD Population. Descriptive statistics will be summarised for cytokines and complement parameters, including the observed value, change from baseline (last pre-dose value on Day 1) and percentage change from baseline for each dose level (cohort) for all time points assessed. In addition to other descriptive statistics, the summary statistics will also include geometric mean in the table.

Mean and individual subject assessment values of cytokines and complement parameters over time will be plotted.

All cytokines and complement data will be presented in the by-subject data listings.

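### Cytokine and complement means at 0.5, 6 and 24 h depend on an undefined 2 h assay trigger, and mean changes are biased upward if that trigger is upward and applied per subject

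*Protocol*

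**What the plan says.** Table 1.1 of the protocol has the same sampling times for both sets of markers. For Panel A (footnote 4): "Serial venous blood samples collected 0 (pre-dose) 0.5, 2, 6, & 24 hours after dosing". For complement (footnote 5): "2 venous blood samples collected 0 (pre-dose), 0.5, 2, 6 & 24 hours after dosing". The 0 and 2 h samples are assayed first, so 0.5, 6 and 24 h are conditional.

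The condition is worded in two ways:

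- The synopsis (Cytokines, and likewise Complement) has "with the remaining samples analyzed only if a change from pre-dose baseline is observed at 2 hours". Section 9.8.2 repeats it as "with the remaining samples analyzed if a change from baseline is observed at 2 hours". No direction is given.
- Section 11.4, the analysis section, has "If cytokine or complement levels are elevated from pre-dose to 2-hours post-dose then all other specified timepoints" being assayed. That is upward only.

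No section gives a size for the change, or says whether one subject's result releases that subject's samples, the cohort's samples, or all analytes.

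SAP section 14 does not refer to staged assay. It reports observed value, change and "percentage change from baseline for each dose level (cohort) for all time points assessed", and adds "Mean and individual subject assessment values of cytokines and complement parameters over time will be plotted". SAP section 3 defines the statistics: "Descriptive statistics will include the number of non-missing values (N), mean, standard deviation (SD), median, minimum, maximum". SAP section 15 rules out imputation. Each healthy-volunteer cohort has 4 active and 2 placebo subjects (SAP 2.5), and placebo is pooled across the five cohorts for reporting (SAP 3).

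SAP section 14 also lists a longer set of Panel A times (adding 15 min, 1, 3 and 48 h) than Table 1.1. That is a separate discrepancy. The protocol times are used here.

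**The concern.** On one curve, the 0 and 2 h points would use every subject and the other points only those whose 2 h result met the condition. Change at 2 h and change at 6 h are both measured from the same pre-dose value. Choosing subjects because their 2 h change was positive therefore tends to choose subjects whose pre-dose value was low by chance. Their change at every other time is then pushed up as well, including at 0.5 h, which precedes the trigger time. A cohort with no cytokine or complement response could show what looks like a sustained rise in the change and percentage-change outputs. Protocol 11.4 places these results under safety and tolerability, so a reader may take such a curve as a signal.

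**Working it through.** The documents give no threshold, variance or sample-size figure for these markers, so there is no plan figure to reproduce. The check derives the bias under no drug effect.

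**Assumptions (not in the documents).** Log level = subject effect + independent error with the same within-subject SD, *sw*, at every time. The trigger is upward and per subject. Then SD of a change = √2·sw, and two changes sharing a baseline have correlation sw²/(2·sw²) = 0.5.

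**1. Bias in mean change.** With *k* the trigger in SDs of the change:

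E[change at 6 h | change at 2 h > k] = 0.5 × φ(k)/(1 − Φ(k))

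- Any rise, k = 0: 0.5 × 0.3989/0.5 = 0.5 × 0.798 = **+0.40 SD** of the change (0.40 × √2 ≈ 0.56 sw).
- Rise above 1 SD, k = 1: 0.5 × 0.2420/0.1587 = 0.5 × 1.525 = **+0.76 SD**.

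The result is the same at 0.5 and 24 h.

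**2. How many subjects.** With any rise as trigger, at least one of 4 active subjects triggers by chance with probability 1 − 0.5⁴ = 0.94. Given that, the conditional mean rests on 4 × 0.5/0.9375 = 2.1 subjects on average. In simulation, mean change was positive in 73% of such groups.

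**3. Percentage terms.** For assumed within-subject CVs of 15%, 30% and 50%, sw = √ln(1 + CV²), and exp(0.564·sw) − 1 gives a spurious geometric rise of about 9%, 18% and 31%. The SAP reports arithmetic mean percentage change. In simulation this was 2.3%, 9.0% and 24.9% with everyone assayed, against 10.9%, 27.0% and 57.7% in subjects with a 2 h rise.

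**4. Other readings of the trigger.**

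| Reading | Bias in mean change, no effect |
|---|---|
| Per subject, any rise | +0.56 sw (+0.40 SD) |
| Cohort mean of 4, any rise | +0.28 sw (0.28/√2 = +0.20 SD) |
| Per subject, either direction, > 1 sw | about 0 (−0.004 sw) |
| Per subject, any rise, errors correlated over time (0.8 per hour) | +0.17, +0.48, +0.34 sw at 0.5, 6, 24 h |

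**5. Observed levels.** With a per-subject any-rise trigger and independent errors, the mean level at conditional times sits only about 0.04 sw above the cohort's baseline mean. Selection acts mainly through low baselines, so the distortion is in change and percentage change.

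**6. Active minus placebo.** With no effect and the same trigger in both arms, each arm is biased by +0.565 sw and the contrast is 0.00. Now suppose a true effect of 1 SD of the change at 2 h. The active arm is then selected at k − 1, with bias 0.5 × φ(k − 1)/(1 − Φ(k − 1)), which is 0.144 at k = 0 and 0.399 at k = 1.

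- No effect at 6 h: contrast 0.144 − 0.399 = −0.255 SD (k = 0), or 0.399 − 0.763 = −0.364 SD (k = 1).
- Effect still 1 SD at 6 h: 1 + 0.144 − 0.399 = 0.745 SD, or 1 + 0.399 − 0.763 = 0.636 SD.

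A real difference is understated.

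**The case against.** The strongest reply is that the upward bias needs two things that the protocol does not say together. First, the trigger must be per subject, and no section names its unit. If one result released everyone's samples, no subset would be selected within a cohort. Section 9.8.2 refers sample processing to a Laboratory Manual that is not among these documents. Second, the trigger must be upward. Three of the four statements of the rule say only that there is a change, and a direction-free trigger gives about zero bias in the mean. Both points stand, so the figures are conditional.

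A reader might infer that the plan is bound to show a rise where none exists. The documents do not support that, for the reasons just given. A reader might also infer a false difference between active and placebo. Under no effect that contrast is unbiased. It is distorted only when a real effect makes selection differ by arm, and the distortion then tends to shrink the difference.

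It is also fair that these are exploratory objectives, absent from the protocol's safety endpoint list (9.7) and stopping rules (6.3). SAP 2.4 disclaims inferential use of the small cohorts. N is a standard statistic, and individual plots and listings are planned, so a falling N could be seen. This limits the consequence. It does not remove the problem, because a reader who sees a smaller N is not told that those subjects were chosen on their 2 h result.

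**Conclusion.** The point holds in conditional form. The trigger's direction, size and unit are undefined, its two wordings conflict, and the SAP's summary rule takes no account of it. Under the only trigger wording in the analysis section (elevated, Protocol 11.4), applied per subject, the SAP's mean changes at 0.5, 6 and 24 h are biased upward under no effect by about +0.40 SD of the change for any rise and +0.76 SD for a rise above 1 SD. This assumes independent equal-variance errors. Correlated errors change the size by time point but leave it positive. The bias is about half as large for any rise in the mean of 4 subjects, and about zero in the mean if direction is ignored. Observed-level means are little affected. The outputs at risk are within-cohort mean change and percentage change for Panel A and complement in healthy volunteers. Panel B in patients is assayed at the sponsor's discretion and lies outside this argument. No trial-level conclusion depends on it: this is a minor correction to an exploratory, descriptive endpoint.

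**What to change.** 1. Reconcile the two wordings in the synopsis, 9.8.2 and 11.4, and state the direction and size of the trigger.
2. Apply it per cohort and analyte: if any of the 6 subjects meets it, assay the remaining samples of all 6, where still available.
3. In SAP section 14, give means and mean plots at 0.5, 6 and 24 h only for cohort-analyte sets in which all subjects were assayed. Show n and label these times as conditional. Let only those sets feed the pooled columns. List everything else.

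**Cost.** Steps 1 and 3 are wording. Step 2 means some extra assays. If the trigger is any rise, 1 − 0.5⁶ = 98% of sets would trigger by chance, so staging would save little. The documents specify frozen storage for the metabolite and urine samples but do not state it for these markers, and SAP 17.2 reports that the Day 113 interim, for which the cytokine and complement tables are marked, was completed in February 2020. Step 2 may therefore no longer be possible. Step 3 works without it.

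**What remains.** Whole cohorts are still selected, so some bias stays: about 0.006 SD of the change for any rise and 0.08 SD for a 1 SD trigger. It grows with larger triggers: at 3 sw (3/√2 = 2.1 SD) it is 0.28 sw, or 0.28/√2 = 0.20 SD. With a sustained 1 SD effect, the active-placebo contrast returns to about 1.0 SD.
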